## 13.2 Subject Discontinuation

A subject may be withdrawn from the study prior to completion for any of the following reasons:

- Whenever the subject decides it is in the subject's best interest to withdraw. NOTE: if the subject decides to withdraw from the study due to an AE then it should be classified as withdrawal due to an AE.
- Whenever the investigator decides it is in the subject's best interest to be withdrawn

- AEs
- Worsening of condition or treatment failure (in the opinion of the investigator)
- Intercurrent illness which may, in the investigator's opinion, significantly affect assessment of clinical status
- Noncompliance
- Pregnancy
- Lost to follow-up
- Sponsor administrative reasons

If a subject withdraws from the study prematurely for any reason, complete the final visit procedures. When a subject is withdrawn from the study for a treatment-related AE (i.e., possibly, probably or definitely related as defined in Section 14), when possible, the subject should be followed until resolution or stabilization of the AE.

Subjects who are prematurely withdrawn or discontinued from the study will not be replaced.

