Test article is defined as a pharmaceutical form of an active ingredient (or "primary operational component" for devices) or vehicle/placebo being tested or used as a reference in the study, whether blinded or unblinded. AEs may be either spontaneously reported or elicited during questioning and examination of a subject. All AEs must be completely recorded on the AE CRF. If known, the investigator should report the diagnosis of the underlying illness or disorder, rather than its individual symptoms. Subjects experiencing AEs that cause interruption or discontinuation of test article, or those experiencing AEs that are present at the end of their participation in the study should receive follow-up as appropriate. If possible, report the outcome of any AE that caused permanent discontinuation or that was present at the end of the study particularly if the AE is considered by the investigator to be treatment-related (i.e., definitely, probably, or possibly related to test article).

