### 14.1 Adverse Event (AE)

All AEs must be recorded on the AE CRF. AEs should be followed to resolution or stabilization (if possible), and reported as serious adverse events (SAEs) if they become serious.

The investigator will instruct the subject to report any AEs that may occur during the study. At each visit, the investigator should ask the subject, in non-directive fashion, about any change in the subject's overall condition since the previous visit.

The severity of each AE, as judged by the investigator, will be recorded on the appropriate AE CRF and will be graded according to the following scale:

Mild - The AE is transient and easily tolerated by the subject.

**Severe -** The AE causes considerable interference with the subject's usual activities, and may be incapacitating or life-threatening.

The investigator must determine the relationship of the AE to the test article according to the following categories:

**Definite** - An event that follows a reasonable temporal sequence from administration of the test article; that follows a known or expected response pattern to the test article; and that is confirmed by improvement on stopping or reducing the dosage, and reappearance of the event on repeated exposure (re-challenge).

**Probable** - An event that follows a reasonable temporal sequence from administration of the test article; that follows a known or expected response pattern to the test article; and that is confirmed by improvement on stopping or reducing the dosage of the test article; and that is unlikely to have been caused by concurrent/underlying illness or other drugs, procedures, or other causes.

**Possible** - An event that follows a reasonable temporal sequence from administration of the test article; that follows a known or expected response pattern to the test article; but may have been caused by concurrent/underlying illness, other drug, procedure, or other causes.

**Unlikely** - An event that does not follow a reasonable temporal sequence from administration of the test article; that does not follow a known or expected response pattern to the test article, or most likely was caused by concurrent/underlying illness, other drug, procedure, or other causes, because of their known effects.

**Not Related** - An event almost certainly caused by concurrent/underlying illness, other drug, procedure, or other causes.

The investigator should categorize the outcome of the AE according to the following categories:

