Fatal - Termination of life as a result of an AE.

Not Recovered/Not Resolved - AE has not improved or the subject has not recuperated.

**Recovered/Resolved** - AE has improved or the subject has recuperated.

IND: 107,302 Protocol: 122-0551-310; v2.0

Recovered/Resolved with Sequelae - subject recuperated but retained the pathological conditions resulting from the prior disease or injury.

**Recovering/Resolving** - AE is improving or the subject is recuperating.

Unknown - Not known, not observed, not recorded or subject refused.

An adverse reaction is any AE caused by a drug. Adverse reactions are a subset of all suspected adverse reactions for which there is reason to conclude that the drug caused the event. For the purposes of prescription drug labeling, the term adverse reaction means an undesirable effect, reasonably associated with the use of a drug that may occur as part of its pharmacological action or may be unpredictable in its occurrence.

A suspected adverse reaction is any AE for which there is a reasonable possibility that the drug caused the event.

For the purposes of IND safety reporting, "reasonable possibility" means there is evidence to suggest a causal relationship between the drug and the AE. A suspected adverse reaction implies a lesser degree of certainty about causality than adverse reaction, which means any AE caused by a drug.

An AE or suspected adverse reaction is considered "unexpected" if it is not listed in the investigator brochure or is not listed at the specificity or severity that has been observed; or, if an investigator brochure is not required or available, is not consistent with the risk information described in the general investigational plan or elsewhere in the current application. For example, under this definition, hepatic necrosis would be unexpected (by virtue of greater severity) if the investigator brochure referred only to elevated hepatic enzymes or hepatitis. Similarly, cerebral thromboembolism and cerebral vasculitis would be unexpected (by virtue of greater specificity) if the investigator brochure listed only cerebral vascular accidents. "Unexpected," as used in this definition, also refers to AEs or suspected adverse reactions that are mentioned in the investigator brochure as occurring with a class of drugs or as anticipated from the pharmacological properties of the drug, but are not specifically mentioned as occurring with the particular drug under investigation.

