#### Adverse Events

Product Name: Halobetasol Propionate Foam, 0.05% IND: 107,302

Sponsor Name: Protocol: 122-0551-310; v2.0

All subjects enrolled in the study who were dispensed and applied test article at least once (Safety population) will be included in the safety analyses based on AE reporting. All AEs reported during the study will be listed, documenting onset, whether therapy was required, any change in test article dosing, severity, possible relationship to test article, and outcome. Verbatim terms on the CRFs will be linked to PTs and SOCs using the MedDRA mapping system. The PTs and SOCs will then be tabulated. All reported AEs will be summarized by the number of subjects reporting AEs, SOC, PT, severity, and relationship to test article by treatment.

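### The outcome definitions in Section 14.1 let an adverse event that is better but still present be recorded as Recovered/Resolved, and the same state also fits two other categories

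*Combined protocol and SAP*

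**What the plan says.** Section 14.1 asks the investigator to assign each AE one of six outcomes: fatal, not recovered, recovered, recovered with sequelae, recovering, or unknown. Three of these definitions matter here:

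- **Recovered/Resolved:** "AE has improved or the subject has recuperated".
- **Recovering/Resolving:** "AE is improving or the subject is recuperating".
- **Not Recovered/Not Resolved:** "AE has not improved or the subject has not recuperated".

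Outcome is a reported field. The Adverse Events paragraph of Section 17.3.2 lists each AE with its onset, whether therapy was needed, and "any change in test article dosing, severity, possible relationship to test article, and outcome". The summary tables described there use system organ class, preferred term, severity and relationship. Outcome is not among them.

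Three places deal with follow-up. Section 13.2 says that after withdrawal for a treatment-related AE, when possible, "the subject should be followed until resolution or stabilization of the AE". Section 14.1 sets the same end point for AEs in general, again where possible. The introductory text of Section 14 adds that "those experiencing AEs that are present at the end of their participation in the study should receive follow-up as appropriate".

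**The concern.** A category named Recovered/Resolved should mean that the event is over. Here its two limbs are joined by *or*, and the first limb asks only for improvement. An AE that is milder than before but still there meets the definition.

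Timing makes this foreseeable. Treatment lasts two weeks, Visit 3 falls at its end, and the last step of that visit in Section 9.3 is to discharge the subject. No later scheduled visit would correct the code. Appendix 4, A 4.5, requires any intolerance to the test article to be recorded as an AE and allows application to be reduced, so events that are better but not gone at Visit 3 are to be expected.

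What is at stake is how the AE listing describes recovery, and whether about 20 sites use the same code for the same state.

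**Working it through.** No arithmetic applies: the plan states no figure on this point. The check is to take the possible states of an AE at the final visit and see which definitions each one meets, reading the Section 14.1 text literally.

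| State at Visit 3 | Recovered/Resolved | Recovering/Resolving | Not Recovered/Not Resolved |
|---|---|---|---|
| A. Ended, subject well | Met | Not met | Not met |
| B1. Still present, better, still improving | Met: it has improved | Met: it is improving | Met if the subject has not recuperated |
| B2. Still present, better, now level | Met: it has improved | Not met on the event limb, since it is not now improving | Met if the subject has not recuperated |
| C. Still present, no better | Not met, unless the subject is judged recuperated | Not met, unless the subject is judged to be recuperating | Met |

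Four things follow.

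1. States B1 and B2 both meet the definition of resolved although the event is present.
2. B1 can meet all three definitions, and B2 can meet two that contradict each other. Section 14.1 gives no order of precedence.
3. For B2 the literal text leads away from Recovering/Resolving and towards Recovered/Resolved, although the event has not ended.
4. The scale is out of order. The category for recovery with sequelae requires that the subject recuperated. Plain Recovered/Resolved does not, because improvement satisfies it.

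Next, where does the code go? Section 17.3.2 sends outcome to the AE listing only. The fields named for that listing include onset but no end date, so those fields would not show which events coded as resolved had actually ended.

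The other outputs do not depend on the code:

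- AE tables count subjects by system organ class, preferred term, severity and relationship.
- The five local skin reactions in Section 10.5 are graded separately at every visit and summarized by severity at Day 15.
- The efficacy analyses use IGA, clinical sign, pruritus and body surface area data.

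**The case against.** The strongest reply is that the labels and verb tenses make the intent plain: *recovered* is finished and *recovering* is under way, so an investigator facing an ongoing AE would choose the latter. Many would. But the written definition permits the other choice, and for an AE that improved and then levelled off the tenses point the wrong way (state B2). The reply reduces how often miscoding will happen; it does not remove the defect.

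A second reply is that little depends on the code. This stands. Outcome is listed rather than tabulated, and no planned test uses it. For telangiectasia, skin atrophy, burning/stinging, folliculitis and edema, persistence at Day 15 is shown by the local skin reaction summaries whatever the AE code says. AEs outside those five have no such cross-check.

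A reader might also infer something stronger: that an event coded as resolved because it improved would drop out of follow-up, since Sections 13.2 and 14.1 name resolution as an end point. The documents do not support this. Section 14 ties follow-up to the AE being present when participation ends, not to its outcome code, and asks sites, if possible, to "report the outcome of any AE that caused permanent discontinuation or that was present at the end of the study". No text ends follow-up because of a code. Sections 13.2 and 14.1 also let follow-up end at stabilization, so an unresolved but stable AE may already be closed. What remains is narrower: the word resolution in those two sections has no definition of its own and could be read through the loose category, so it should be reconciled.

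**Conclusion.** The definition is wrong as written; the severity is minor. An AE that is better but still present can be recorded as Recovered/Resolved, and the same state can also fit Recovering/Resolving and Not Recovered/Not Resolved. Compliant sites can therefore code it differently, and the outcome field of the AE listing can overstate recovery.

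The number of AEs affected cannot be estimated: the documents give no expected AE rate and no proportion open at Visit 3. The upper bound is every AE that has improved but is ongoing at the last visit. Both arms share the definitions. AE incidence, local skin reaction summaries and efficacy are unaffected, and no loss of follow-up is established.

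The conclusion rests on a literal reading of the three definitions and on no other text in the documents giving a rule for choosing between them. Training material outside the documents could narrow the ambiguity in practice.

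**What to change.** In Section 14.1, make the three categories mutually exclusive:

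- **Recovered/Resolved:** the AE is no longer present, or the condition has returned to its pre-AE state.
- **Recovering/Resolving:** the AE has improved or is improving but is still present.
- **Not Recovered/Not Resolved:** the AE is still present and has not improved.

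All three lines need to change. Rewording only the first two would leave an overlap, because an improved AE in a subject who has not recuperated would still meet the present Not Recovered/Not Resolved line. Under the new wording, state A falls only in the first category, B1 and B2 only in the second, and C only in the third.

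Then reconcile the word resolution in Sections 13.2 and 14.1 with these definitions, so that the follow-up text and the outcome code use the term in one sense.

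The cost is three definition lines, a cross-reference in two sections, and the same wording wherever sites are told how to complete the AE form. Slightly more AEs will be listed as ongoing. No visit, endpoint, dose or analysis changes. The change is best made before AEs are coded, because the listing fields named in Section 17.3.2 would not allow a later correction.

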# 14.2 Serious Adverse Event (SAE)

An event that is serious must be recorded on the AE CRF and on the TI SAE Report Form, and requires expeditious handling to comply with regulatory requirements.

An AE or suspected adverse reaction is considered "serious" if, in the opinion of either the investigator or Sponsor, it results in any of the following outcomes:

- Death.
- Life-threatening event.
- Inpatient hospitalization or prolongation of existing hospitalization.

- Persistent or significant incapacity or substantial disruption of the ability to conduct normal life functions.
- Congenital anomaly/birth defect.
- Is an important medical event defined as a medical event(s) that may not result in death, be life-threatening, or require hospitalization but, based upon appropriate medical judgment, may jeopardize the patient/subject and may require medical or surgical intervention to prevent one of the outcomes listed in the definition above. Examples of such medical events include allergic bronchospasm requiring intensive treatment in an emergency room or at home, blood dyscrasias or convulsions that do not result in inpatient hospitalization, or the development of drug dependency or drug abuse.

Events NOT considered to be serious AEs are:

- Hospitalizations for the treatment, which was elective or pre-planned, of a preexisting condition that did not worsen, and
- Treatment on an emergency, outpatient basis, for an event not fulfilling any of the definitions of "serious" given above and not resulting in hospital admission.

AEs classified as "serious" by either the investigator or the Sponsor require expeditious handling and reporting to TI to comply with regulatory requirements. All serious AEs, whether related or unrelated to test article, must be immediately reported by telephone to the Medical Monitor and, in the event that he/she is unavailable, to the Project Manager listed on the first page of the protocol. Written notification of all SAEs should be sent to the Project Manager by email or confirmed facsimile transmission. These include those SAEs listed in the protocol or investigator brochure and must include an assessment of whether there is a reasonable possibility that the drug caused the event.

Study endpoints that are SAEs (e.g., all-cause mortality) must be reported in accordance with the protocol unless there is evidence suggesting a causal relationship between the drug and the event (e.g., death from anaphylaxis). In this case, the investigator must immediately report the event to the Sponsor. In addition, such information should also be provided to the site's respective IRB per their governing guidelines for SAE reporting.

If only limited information is initially available, follow-up reports are required. Should the investigator become aware of a SAE (regardless of its relationship to test article) that occurs within 30 days after stopping the test article, the SAE must be reported in accordance with procedures specified in this protocol. In the event of death, if an autopsy is performed, a copy of the report should be sent to TI, if available.

As required, TI will notify participating investigators of all suspected adverse reactions that are serious and unexpected. This notification will be in the form of an IND safety report of potential serious risks as soon as possible but no later than 15 calendar days after the Sponsor determines that the information is "reportable" according to the criteria listed in 21 CFR Section 312.32. These are:

i) Serious and unexpected suspected adverse reactions,

- ii) Findings from other studies including epidemiological studies, pooled analyses or other clinical studies that suggest a significant risk in humans exposed to the test articles,
- iii) Findings from animal or in vitro tests that suggest a significant risk to humans exposed to the test articles, or reports of significant organ toxicity at or near the expected human exposure, and
- iv) Clinically important increases in the rate of occurrence of serious suspected adverse reactions.

Upon receiving such notices, the investigator must review and retain the notice with the Investigator Brochure and immediately submit a copy of this information to the responsible IRB according to local regulations. The investigator and IRB will determine if the informed consent requires revision. The investigator should also comply with the IRB procedures for reporting any other safety information. Where required, submission of safety updates by the investigator to Health Authorities should be handled according to local regulations.

### 14.3 Pregnancy

WOCBP include any female who has experienced menarche or is 10 years of age or older and who has not undergone successful surgical sterilization (hysterectomy, bilateral tubal ligation, or bilateral oophorectomy) or is not postmenopausal [defined as amenorrhea >12 consecutive months in women 55 years of age and older]. Even women who are using oral, implanted, or injectable contraceptive hormones, an IUD, barrier methods (diaphragm and spermicidal, condom and spermicidal) to prevent pregnancy, practicing abstinence, or where the partner is sterile (e.g., vasectomy performed at least six months prior to the subject's initiation of treatment) and the subject states she is in a monogamous relationship, should be considered to be of childbearing potential. Surgical means of sterilization (e.g., vasectomy, tubal ligation) must be a minimum of six months post-procedure to be considered effective birth control.

WOCBP must have a negative pregnancy test prior to study enrollment and must use an effective method of contraception during the course of the study, in a manner such that risk of failure is minimized. Prior to study enrollment, WOCBP must be advised of the importance of avoiding pregnancy during trial participation and the potential risk factors

<sup>14 Effective forms of birth control include hormonal contraceptives [oral, injectable, transdermal or intravaginal] or intrauterine device (IUD) for two cycles (e.g., 8 weeks) (note: for Depo-Provera the requirement is at least 7 days after injection) prior to test article application, condom and spermicidal or diaphragm and spermicidal). Other acceptable forms of birth control include: a) abstinence for subjects who are not sexually active or b) if the subject is in a monogamous relationship with a partner who is sterile (e.g., vasectomy performed at least six months prior to the subject's initiation of treatment). Subjects who become sexually active or begin to have relations with a partner who is not sterile during the trial must agree to use an effective form of birth control for the duration of the study.

for an unintentional pregnancy. The subject must sign an informed consent form documenting this discussion.

WOCBP should be instructed to contact the investigator immediately if they suspect they might be pregnant (e.g., missed or late menstrual period). If a subject or investigator suspects that a subject may be pregnant at any time during the study the test article must be withheld until the results of laboratory pregnancy testing are available. If pregnancy is confirmed, the subject must not receive or apply further test article and must be discontinued from the study.

If following initiation of study treatment, it is subsequently discovered that a trial subject was pregnant or may have been pregnant at the time of test article exposure, the investigator must immediately notify the Medical Monitor of this event, and record the pregnancy on the appropriate pregnancy surveillance form. The form will be sent to TI. The investigator must notify the IRB of any pregnancy associated with the study therapy and keep careful source documentation of the event.

Protocol-required procedures for those subjects that are discontinued from the study must be performed on the subject unless contraindicated by pregnancy (e.g., x-ray studies). Other appropriate pregnancy follow-up procedures should be considered if indicated, including counseling of the subject by the investigator and her managing physician or health care provider (e.g., obstetrician). In addition, the investigator must report to TI, on the appropriate TI pregnancy surveillance form(s), any follow-up information regarding the course of the pregnancy, including perinatal and neonatal outcome. Although pregnancy itself is not an AE, any complications during pregnancy should be recorded as AEs (or SAEs – if they fulfill the SAE criteria). Offspring should be followed for a minimum of eight weeks. Any congenital anomaly/birth defect in a child born to a subject exposed to the test article(s) should be recorded as a SAE and details documented in the pregnancy surveillance form. Abortion, whether accidental, therapeutic or spontaneous should be reported as a SAE.

